True negative case: CT-FFR negative and CATH-FFR negative

Proportion of correct CT-FFR triage = (True positive + True negative) / All CATH

SOC group:

True positive case: SOC chosen by attending physician for CATH confirmed by CATH-FFR. By definition, the clinicians' decision to CATH based on clinical evidence is considered an SOC positive case, there can be no SOC true negative cases that go to CATH.

Proportion of correct SOC triage = True positive / All CATH

2. Safety: Patients following CT-FFR-guided management will have similar MACE rates, including death, ACS and unanticipated late revascularization when compared to SOC-guided patients.

Methods

Study Population

The study population will be drawn from ED ACP who have already undergone CCTA for diagnosis, and have been found to have 50% or greater stenosis but less than 90% of at least one coronary branch. Two-hundred patients meeting entry criteria will be enrolled from a sample of ED ACP patients at Beaumont Hospital (Royal Oak). These patients will be randomized 1:1 using sealed envelopes provided by the study statistician, to either standard of care (SOC) or CT-FFR management. (See Figure 1. Study Diagram)

Inclusion Criteria

1. Emergency department or inpatients admitted through the ED with chest pain suspicious for ACS based on history and physical examination.
2. At least one biomarker (troponin) and electrocardiogram with no evidence of definite ACS.
3. A completed CCTA demonstrating $\geq 50\%$ but $< 90\%$ stenosis of at least one coronary artery branch.
4. CCTA test images with sufficient diagnostic quality for CT-FFR analysis.
5. Ability and willingness to provide informed consent.

Exclusion Criteria

- 1 Left main coronary stenosis of 50% or greater.
- 2 CCTA lesions demonstrating stenosis >90% ("subtotal"), or complex, high-risk plaque characteristics resulting in an a priori recommendation for triage to CATH by CCTA interpreting physician.
- 3 Attending physician a priori decision for CATH.
- 4 Prior coronary stent, coronary bypass or prior known myocardial infarction.
- 5 Clinical instability, such as hypotension, signs of shock, and/or unrelieved or accelerating chest pain.
- 6 Pregnancy

Obtaining Consent

Consent will be obtained by a co-investigator. Patients will have at least 20 minutes to consider whether they wish to consent.

Screening Log

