If attending physicians decide that study patients should undergo CATH, the protocol will specify that CATH-FFR will be performed on all lesions over 30% stenosis severity, to confirm the presence or absence of flow-limiting stenosis prior to coronary intervention or triage to medical therapy. This may be waived without protocol deviation if deemed unsafe due to the severity of stenosis or due to other clinical circumstances, as documented on the Physician Study Questionnaire.

Clinical Follow-up

Patients will be followed at 1 month, 3 month and 1 year using a chart review and structured telephone interviews. Permission will be requested from patients for examination of outside medical records including office records and hospital records related to coronary artery disease.

Risks of the Study

Both the SOC and CT-FFR management strategies are currently used routinely at Beaumont Health, where ED patients' diagnostic strategy is selected according to the preference of their individual attending physician. There is no risk from the research study associated with CCTA testing, as patients will already have completed a clinically ordered CCTA test prior to their eligibility for the study.

Both SOC and CT-FFR Group patients will undergo CATH if indicated by the results of noninvasive evaluation by CT-FFR or SOC physicians' clinical judgment. Based on the baseline year prior to CT-FFR (Sept. 2014 – Aug. 2015), the CATH rate in SOC group patients was 58%. The CATH rate in CT-FFR patients during the previous research period (IRB #2016-157) from Sept. 2015 – Dec. 2016 was similar, at 79/147 patients, or 54%. Thus, the risk from the incidence of CATH was similar in the two groups. The study protocol does require CATH-FFR in patients undergoing CATH (unless there are no lesions >30%). There is a theoretical risk of rare (<1%) vascular injury due to the CATH-FFR catheter, however, CATH-FFR is a standard clinically recommended procedure prior to revascularization in CATH patients to insure accurate diagnosis of flow-limiting stenosis. If attending physicians believe there is a clinical reason that CATH-FFR should not be done, such as a lesion that is too severe, it may be omitted without protocol deviation, as long as the reason is documented in the Physician Study Questionnaire. The additional radiation risk added by CATH-FFR is estimated at <1 mSv, equivalent to <1 year of annual background radiation from environmental sources.

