Risks Associated with Heart Catheterization and Invasive Fractional Flow Reserve

Common (more than 10%)

- warm feeling or flushed feeling during adenosine infusion (which is part of the FFR study)
- lightheadedness
- nausea
- pain
- discomfort
- bruising or bleeding where the catheter is inserted in the groin
- radiation equivalent to 3-5 years of natural background radiation

Rare (less than 1%)

- contrast (dye) allergy
- diaphoresis (temporary excessive sweating)
- atrioventricular block -impaired conduction of the impulse that regulates the heartbeat (from adenosine)
- contrast induced nephropathy (deterioration of kidney function due to contrast exposure)
- hives (for those allergic to contrast dye)
- thrombosis (blood clots resulting in reduced blood flow)
- artery dissection (damage to the artery wall)
- perforation (a hole in the artery)
- stroke
- myocardial infarction (heart attack)
- death

Internal Safety Monitoring Committee

An Internal Safety Monitoring Committee will conduct regularly scheduled reviews of the safety of patients. Two physicians and a statistician who are not co-investigators will be included. Members will monitor safety outcomes, enrollment and completeness of follow-up. The Committee will meet after the first 20 patients and after each 40 subsequent patients till the study is completed. Any MACE event or major adverse outcome will be reported immediately to the Committee. The results of all Committee meetings will be provided to the IRB.

Data Analysis

Descriptive statistics will be given for all variables collected including indications for the test, demographics, patient history, CTA tech information, details from the physicians reading form, and from the CT-FFR. Missing data will remain missing and will not be replaced by substitutions or interpolation. Categorical variables will be summarized as counts and percentages. All continuous variables will be

summarized as means+/- the standard deviation where normal or median and 25th, 75th percentiles if not normal. The minimum and maximum will also be provided.

Catheterization Rate: The primary outcome will be examined between the 2 randomization arms using Pearson's Chi-square test. The Odds ratio and 95% confidence interval will also be reported.

Diagnostic Effectiveness: The secondary outcome will be defined as the proportion of accurate triage using CATH-FFR as the gold standard among all patients triaged to CATH by each strategy.

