The SOC group will be analyzed according to actual triage decisions, as well as the hypothetical results of triage using a blinded CT-FFR analysis collected on those patients. The accuracy of triage between these two methods will then be compared.

Safety: The secondary outcome will be safety, as defined by the incidence of death, ACS or late unscheduled revascularization in each group.

Additional data analysis:

The Total length of stay, with sub-analysis of ED and inpatient length of stay will be reported as medians, 25th and 75th percentiles and minimum to maximum. The 2 randomization arms will be examined for each of these using Wilcoxon rank sum tests.

The hospital admission rate, the proportion of patients going to CATH in either arm who are found to have significant coronary stenosis (>50 stenosis), proportion of patients going to CATH who have a positive invasive FFR, percentage of patients undergoing PCI or CABG within 3 months, secondary diagnostic testing during index visit or within 3 months follow-up, including: recurrent ED visits, inpatient admissions for suspected acute coronary syndromes and/or CATH, outpatient or inpatient evaluation with cardiac CCTA or stress testing, cardiac surgery or PCI and MACE events (including all cause death, acute myocardial infarction, acute coronary syndromes, unscheduled revascularization after index visit) will be examined between the 2 arms using Pearson's Chi-square test where appropriate (Expected frequency>5 in all cells), otherwise Fisher's Exact tests will be used. The Odds ratios and 95% confidence intervals will also be reported.

[figure not shown]
Estimated costs of care: including all estimated charges based on Beaumont hospital analysis multiplied by the standard Medicare cost/charge ratio will be reported as medians, 25th and 75th percentiles and minimum to maximum. The 2 randomization arms will be examined using Wilcoxon rank sum tests.

We may explore possible associations between patient characteristics demographics, prior history or testing indications and the randomization groups, safety outcomes,

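### Apart from death and MI, the catheterization harms the protocol lists are in no planned between-arm analysis, although the arms are planned to differ in catheterization exposure

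*Combined protocol and SAP*

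**What the plan says.** Three places define safety, and they largely agree.

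- Secondary Hypotheses, item 2: "Patients following CT-FFR-guided management will have similar MACE rates, including death, ACS and unanticipated late revascularization when compared to SOC-guided patients".
- Data Analysis, Safety: "The secondary outcome will be safety, as defined by the incidence of death, ACS or late unscheduled revascularization in each group".
- Additional data analysis, among the items compared between arms by chi-square or Fisher's exact test with odds ratios and 95% CIs: "MACE events (including all cause death, acute myocardial infarction, acute coronary syndromes, unscheduled revascularization after index visit".

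Two places describe the harms of the invasive procedures.

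- Risks of the Study: "There is a theoretical risk of rare (<1%) vascular injury due to the CATH-FFR catheter".
- Risks Associated with Heart Catheterization and Invasive Fractional Flow Reserve. The band above 10% includes "bruising or bleeding where the catheter is inserted in the groin" and radiation. The band below 1% includes "contrast induced nephropathy (deterioration of kidney function due to contrast exposure", contrast allergy, AV block, thrombosis, dissection, perforation, stroke, "myocardial infarction (heart attack" and death.

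Both group-management sections specify CATH-FFR on lesions above 30% stenosis in patients who go to CATH, with a documented waiver allowed. The Internal Safety Monitoring Committee is told at once of any MACE event or major adverse outcome. The second term is not defined, and no tabulation by arm is stated.

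**The concern.** The primary outcome is the CATH rate, so the arms are meant to differ in how many patients are exposed to the procedure. The harms that follow from deferring CATH (ACS, late unscheduled revascularization) are in the safety outcome. Most of the harms that follow from doing CATH are not. If CT-FFR lowers the CATH rate, a reader of the results would see any added deferral events but no count of bleeding, vascular injury, stroke or nephropathy in either arm. Nor would a reader learn how often CATH-FFR, which the protocol specifies for both arms, led to vascular injury, although the protocol singles that risk out.

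**Working it through.** **Step 1. Listed harms against planned between-arm analyses.**

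| Harm on the protocol's CATH/CATH-FFR list | Compared by arm? |
|---|---|
| Death | Yes, from any cause |
| Myocardial infarction | Yes, through ACS and acute MI in the MACE list |
| Access-site bruising or bleeding | Not named |
| Dissection, perforation, thrombosis | Not named |
| Stroke | Not named |
| Contrast nephropathy, contrast reaction | Not named |
| AV block | Not named |
| Radiation | Only an optional exploration against patient characteristics |

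**Step 2. The plan's own figures.** Sample Size uses a 2:1 mix of the 51-70% and 71-99% stenosis groups.

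- SOC: (2 × 58.3 + 89.5)/3 = 68.7%
- CT-FFR: (2 × 21.3 + 65.6)/3 = 36.1%

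The named method is a two-sided Z-test with unpooled variance, alpha 0.05 and 90% power: n = (P1Q1 + P2Q2)(1.960 + 1.282)² / (P1 − P2)². For 0.687 versus 0.45 this is (0.2150 + 0.2475) × 10.51 / 0.0562 = 86.5, so 87 per arm. The other two rows give 44 and 59. All three match the table.

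**Step 3. Difference in exposure, per 100 patients per arm.**

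- Most conservative planning case: 68.7 − 45.0 = 23.7 fewer CATHs
- Anticipated case: 68.7 − 36.1 = 32.6 fewer CATHs
- Historical rates in Risks of the Study: 58% versus 79/147 = 54%, about 4 fewer CATHs

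**Step 4. Expected patients with a harm.** Only patients who undergo CATH are at risk, so the expected count per 100 is 100 × CATH rate × harm per CATH. The documents give bands, not rates, so I use the band limits: 1% (top of the rare band) and 10% (bottom of the common band).

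| Harm per CATH | SOC | CT-FFR | Difference, planning rates | Difference, historical rates |
|---|---|---|---|---|
| 1% | 0.69 | 0.36-0.45 | 0.24-0.33 | 0.04 |
| 10% | 6.9 | 3.6-4.5 | 2.4-3.3 | 0.4 |

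**Step 5. What 100 per arm could show.**

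- At 1% per CATH, Fisher's exact test has power below 0.1%. About 7,600 to 15,800 patients per arm would be needed for 80% power (two-sided 5%, normal approximation).
- At 10% per CATH, Fisher power is 6-10%, and about 730 to 1,500 per arm would be needed.
- The 95% CI at 10% per CATH is wide. For 6.87% versus 3.6%, SE = √[(0.0687 × 0.9313 + 0.036 × 0.964)/100] = 0.0314. The difference is 3.3 points with a CI of about −2.9 to 9.4. For 6.87% versus 4.5%, SE = 0.0327, and the difference is 2.4 points with a CI of about −4.0 to 8.8.

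**The case against.** A reader might infer that the safety outcome counts no procedural harm at all, and so could never credit CT-FFR with a complication avoided. The documents do not support that. Death and MI are on the protocol's own CATH risk list and are counted whatever their cause.

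A reader might also infer that the omitted events could reverse the safety comparison. That would need rates the documents do not give. If one assumes 1-3% serious complications per CATH, the arm difference is 23.7 × 1% to 32.6 × 3%, or 0.24 to 0.98 patients per 100. That is under one patient, and it could change a sign only if the MACE difference were equally small.

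Further arguments for the plan as written:

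- *Avoided CATH is already the primary outcome, and MACE is the check on deferral.* This is a coherent division. Admissions, length of stay, cardiac surgery and costs are also compared and may pick up some serious complications. But a CATH count is not a complication count, and those measures are indirect.
- *The protocol itself calls the CATH risk of the two strategies similar (58% versus 54%).* The figure belongs in the range. However, the CT-FFR figure comes from a registry cohort with 25-99% stenosis, and the trial is sized for a much larger difference.
- *The Committee reviews safety on a schedule, and all collected variables will be described.* Neither provision names these complications or requires a count by arm.
- *A comparison of arms cannot isolate the effect of CATH-FFR.* This stands, because both arms receive it. It calls for a pooled count instead.
- *The added outcome would be underpowered.* This also stands, and it limits the request to description.

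**Conclusion.** The gap is real but modest. Apart from death and MI, the listed CATH and CATH-FFR harms are in neither the safety outcome nor any planned between-arm analysis. The planned difference in exposure is 23.7 to 32.6 CATHs per 100 patients, or about 4 per 100 on the historical rates.

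The expected numbers are small. Any single harm at or below 1% per CATH gives under one patient per arm. A harm at 10% gives about 6.9 versus 3.6 to 4.5 per 100. These figures assume that the planning CATH rates hold, that only catheterized patients are at risk, and that the harm rates sit at the band limits.

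The conclusion concerns what the plan names. The data forms are not part of the documents, so some of these events may be recorded without being analysed. Counting these harms would make the safety account two-sided. It would not let the trial conclude that either strategy is safer on balance.

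**What to change.** Keep the MACE outcome as it is. Add the following to Secondary Hypotheses (Safety) and Data Analysis (Safety):

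1. A prespecified descriptive outcome: the number and percentage of all randomised patients, by arm through 3 months, with a clinically documented CATH or CATH-FFR complication from the protocol's risk list. Show major items separately from access-site bruising, with a 95% CI for the arm difference.
2. CATH-FFR complications among all patients who had CATH-FFR, with both arms pooled.
3. The same table for the Internal Safety Monitoring Committee.

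A net composite of MACE or major procedural complication may be shown, labelled as descriptive. No claim of net benefit should rest on it.

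The cost is short wording and a few data fields, defined in advance and filled from the chart review and telephone interviews already planned at 1 and 3 months. No laboratory tests are added, so nephropathy would be counted only where it was clinically documented and may be under-recorded. Events will be sparse and the intervals wide.

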In September 2015, a new FDA-approved test became available at Beaumont, computed tomography-derived fractional flow reserve (CT-FFR, provided by HeartFlow, Inc.), that provides flow information directly from computational fluid dynamic analysis of CCTA images without further testing^{7- 15}. This analysis does not involve any additional imaging, contrast or medications. CT-FFR has been shown to be more accurate in predicting the presence of true ischemia on invasive fractional flow reserve testing in the invasive catheterization laboratory (CATH-FFR). Patients managed by CATH-FFR have been shown to have better outcomes than patients managed using visual inspection of CATH stenosis alone. The standard cutoff for an abnormal CATH-FFR and CT-FFR is the measurement of a blood pressure drop of $\geq 20\%$ (FFR ≤ 0.80) across a given stenosis.

For Beaumont ED patients, CT-FFR has been in use on a research basis since September, 2015, but is not considered standard of care. Since September 2015 we have conducted a study to analyze clinical outcomes after CT-FFR, (a sub-analysis of HIC #2016-157, the Beaumont CT Registry). We have collected, analyzed data and submitted for publication, data on 147 ED patients with CCTA stenosis of 25-99% managed with CT-FFR and followed for a minimum of 90 days. These data show no evidence to date of increased risk, but do show improved prediction of the need for revascularization using CT-FFR (see Appendix, submitted for publication).

The objective of the present trial is to evaluate the CATH rate and diagnostic effectiveness of CT-FFR as compared to a standard of care diagnostic strategy (SOC) in the management of ACP patients with intermediate-to-severe stenosis on CCTA.

Hypotheses:

Primary Hypothesis:

Cardiac Catheterization Rate: Use of CT-FFR will reduce the CATH rate in ACP patients with >50% stenosis on CCTA. There will be a pre-specified subset analysis of the Intermediate (51-70%) and Severe (71-90%) stenosis groups.

Secondary Hypotheses:

1. Diagnostic Effectiveness: CT-FFR results will more accurately triage patients to CATH compared to patients triaged by SOC. True flow-limiting coronary stenosis will be defined by CATH-FFR as the gold standard in patients undergoing CATH. Accurate triage will be calculated as the proportion of patients with correct triage to CATH based on CATH-FFR results:

CT-FFR group:

True positive case: CT-FFR positive and CATH-FFR positive

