Attending physicians will dictate SOC management according to their own clinical judgment. This could include discharge without further testing, EKG-only stress testing, stress echocardiography, stress myocardial perfusion imaging, direct admission and further noninvasive testing or CATH. In addition to standard testing, a blinded CT-FFR will be obtained for post hoc analysis, but it will not be used for patient management. Image data from our CT workstation will be sent directly to HeartFlow, Inc. over a secure research transfer node.

If attending physicians decide that SOC Group patients should undergo CATH, the protocol will specify an invasive fractional flow reserve will be performed on all lesions over 30% stenosis severity, to confirm the presence or absence of flow-limiting stenosis. This may be waived without protocol deviation if deemed unsafe by the severity of stenosis or due to clinical circumstances, as documented in a completed Physician Study Questionnaire.

CT-FFR-Guided Group Management

Patients in this group will be triaged using CT-FFR. Image data from our CT workstation will be sent directly to HeartFlow, Inc. over a secure Priority (STAT) transfer node. Interpreting physician will categorize CT-FFR results as follows:

1. CT-FFR >0.80. All CT-FFR segmental values are >0.80, with no indication of flow limiting ischemia. A non-binding recommendation that the patient undergo an initial trial of medical therapy will be made by the interpreting co-investigator. Attending physicians will be asked to complete a study Physician Questionnaire to determine whether they followed this recommendation or not, and if not, why not.
2. CT-FFR 0.70-0.80. These will be reported as values in the abnormal range without specific recommendations about whether CATH should be performed. Attending physicians will decide triage in consideration with other clinical data. Attending physicians will be asked to complete a study Physician Questionnaire to determine what clinical factors influenced their triage decision.

3. CT-FFR <0.70. These are abnormal values that are will be reported as high-risk. A non-binding recommendation that the patient undergo CATH will be made by the interpreting co-investigator. Attending physicians will be asked to complete a study Physician Questionnaire to determine whether they followed this recommendation or not, and if not, why not.

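### The cost comparison has no rule for CT-FFR charges, so the CT-FFR strategy may never be charged for its own test

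*Combined protocol and SAP*

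**What the plan says.** The cost outcome is listed in Data Analysis, among the additional analyses. It is defined as "including all estimated charges based on Beaumont hospital analysis multiplied by the standard Medicare cost/charge ratio", summarised by medians, quartiles and range, and tested: "The 2 randomization arms will be examined using Wilcoxon rank sum tests". No rule says how research-only procedures are to be treated.

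SOC Group Management adds a test to the SOC arm: "In addition to standard testing, a blinded CT-FFR will be obtained for post hoc analysis, but it will not be used for patient management". Those images travel "over a secure research transfer node". Under CT-FFR-Guided Group Management the images travel "over a secure Priority (STAT) transfer node", and the result guides triage. In both arms the analysis is done by an outside company. The introductory background says that CT-FFR for emergency department patients has been used on a research basis and "is not considered standard of care".

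On invasive measurement, SOC Group Management states that if CATH is done, "the protocol will specify an invasive fractional flow reserve will be performed on all lesions over 30% stenosis severity", and the CT-FFR arm has the same requirement. Both sections allow a documented waiver. Risks of the Study exempts patients with no lesion above 30% and describes CATH-FFR as standard, clinically recommended practice before revascularization.

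**The concern.** A cost comparison of two strategies should charge each strategy for what it needs and for nothing that only the trial adds. CT-FFR is needed in one arm and is a research extra in the other. A rule that simply sums hospital charges gives the right contrast only if the SOC test generates no charge and the CT-FFR-arm test does. The plan neither states this nor makes sure of it.

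If the condition fails, the cost of the test under study disappears from the comparison. A reported saving would then reflect fewer downstream procedures without the price of the test that produced the reduction. Changing the summary statistic or the test would not help, because the input charges would be wrong for the question.

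**Working it through.** **Figures that can be reproduced.** The plan gives no figure for cost. The design figures that enter here are the planned CATH rates in Sample Size, weighted 2:1 across the stenosis groups:

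- SOC: (2 × 58.3 + 89.5)/3 = 68.7%, as stated.
- CT-FFR: (2 × 21.3 + 65.6)/3 = 36.1%, as stated.
- The table's 87 per arm for 68.7% versus 45% also reproduces: (1.960 + 1.282)² × (0.687 × 0.313 + 0.45 × 0.55)/0.237² = 86.5, rounded up to 87.

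**Step 1: the CT-FFR charge.** Let T be the cost of one CT-FFR analysis. Let b be the share of CT-FFR-arm patients, and a the share of SOC patients, for whom it appears in the charges. The strategy contrast (CT-FFR minus SOC) should contain T × (1 − 0) = T. The charge data contain T × (b − a). The error is therefore −T × (1 − b + a).

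- Charged in both arms (b = 1, a = 1): error −T.
- Charged in neither (b = 0, a = 0): error −T.
- Charged in the CT-FFR arm only (b = 1, a = 0): error 0.

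Nothing in the documents suggests charging in the SOC arm only, so that case is set aside. In the first two cases the error favours CT-FFR.

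**Step 2: does the planned analysis protect against this?** No. A constant T added to, or removed from, every patient in an arm moves that arm's median and quartiles by exactly T. The median difference is therefore off by T, as the mean difference is. The rank sum test gives the same result for the first two cases, because a constant common to both arms leaves the ranks unchanged.

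**Step 3: can it change the conclusion?** The documents give no unit costs, so this is illustration only. Assumptions: base cost lognormal with median 3000; CATH adds a lognormal cost with median 8000; log-SD 0.5 for both; 100 per arm; 1000 runs; two-sided 5% test. CATH-FFR is not modelled separately. The table shows the percentage of runs in which the rank sum test rejects.

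| T | CATH 68.7% vs 45%: T in both arms | CATH 68.7% vs 45%: T in CT-FFR arm only | Equal CATH 68.7%: T in both arms | Equal CATH 68.7%: T in CT-FFR arm only |
|---|---|---|---|---|
| 500 | 81.7 | 57.7 | 3.9 | 10.6 |
| 1000 | 79.5 | 27.9 | 3.9 | 25.1 |
| 1500 | 80.6 | 12.3 | 5.0 | 47.4 |
| 2000 | 79.9 | 5.2 | 5.5 | 69.2 |

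In the last column nearly all rejections show CT-FFR as dearer, which is correct when it averts no CATH. Under these assumptions the charging rule decides the answer.

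**Step 4: CATH-FFR.** Let F be the added cost of a CATH-FFR and u the share that usual care would have done anyway. The trial-induced excess in SOC is (1 − u) × F × (SOC CATH rate − CT-FFR CATH rate). The upper limits, with u = 0 and a CATH-FFR at every CATH, are:

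- Planning rates, 68.7% vs 36.1%: 0.326F per patient.
- Planning rates, 68.7% vs 45%: 0.237F.
- Historical rates in Risks of the Study, 58% vs 54%: 0.04F.

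The waiver, the 30% limit and any u above 0 reduce all three. The 36.1% also comes from CT-FFR negative patients only, so it may understate the rate in the whole CT-FFR arm.

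**The case against.** The strongest reply is that the plan is silent on billing, and silence is not an error. The outcome is headed as costs of care, and a blinded analysis barred from management is not naturally care. The two arms use different transfer routes, and Risks of the Study says both strategies are in routine use at the hospital. All of this fits billing in the CT-FFR arm only, in which case nothing is wrong. That much stands: a reader might infer that the cost comparison is biased as written, and the documents do not show it. But a transfer route is not a billing rule. With an outside vendor and a test described as research use, CT-FFR may be absent from hospital charges in both arms.

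A reader might also infer that every CATH carries a trial-imposed CATH-FFR, that this cost falls more heavily on SOC, and that both effects favour CT-FFR. The documents do not support this:

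- The requirement has a lesion threshold and a waiver.
- The plan itself calls the procedure standard before revascularization, so part of its cost is ordinary care.
- The difference nearly vanishes at the historical CATH rates. That cohort had 25-99% stenosis and is not the trial population, but its rates belong in the range.
- CATH-FFR is done before the choice between intervention and medical therapy, so it may avert interventions and lower later charges, possibly more in the arm with more CATHs.

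Finally, no hypothesis, sample size or stated decision rests on cost. That is correct, and it sets the priority.

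**Conclusion.** The concern holds in conditional form. The rule of summing all charges, applied to a trial that runs CT-FFR in both arms, does not ensure that the CT-FFR strategy is charged for its own test. The error is up to 1.0T per patient in favour of CT-FFR if the test is charged in both arms or in neither, and zero if it is charged in the CT-FFR arm only. The documents do not say which applies and do not give T. The simulation shows that the choice could matter, but only under its assumed costs.

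CATH-FFR is a minor and uncertain addition: at most about 0.04F to 0.33F per patient in gross procedure cost, with no established net direction. Severity is low, because cost is a formally tested additional analysis but not a primary or secondary hypothesis.

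**What to change.** In the cost paragraph of Data Analysis, state two things before results are seen:

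- CT-FFR is costed to every CT-FFR-arm patient at one stated unit price, whoever paid for it.
- The blinded research CT-FFR is excluded from SOC costs.

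A sensitivity analysis that omits CATH-FFR charges from both arms is optional. If it is done, the report should say that it also removes some ordinary care costs and leaves any downstream effect of CATH-FFR in place.

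The cost is a few lines of SAP text and a little costing work, with no new patient data and no change to care. The downside is that the apparent saving from CT-FFR may be smaller.
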